6.3 Mass Balance Population

The mass balance population will be defined for Part 2 and will include all subjects who have received 1 dose of IMP in Part 2 and who have evaluable total radioactivity concentration (urinary and/or faecal) data and who have no protocol deviations that may affect the mass balance analysis. Such protocol deviations would include anything that affects the accurate measurement of the amount of urine/faeces collected or any AEs that may affect the mass balance analysis, for example:

- spillage of urine and/or faeces
- missing collections
- AEs that may affect the mass balance analysis, such as vomiting of the dose

The mass balance population will be confirmed by Quotient with approval from Kadmon once all urinary and faecal data have been received.

If required, a mass balance analysis dataset or datasets may also be documented by Quotient with approval from Kadmon at the same time as the mass balance population. The mass balance analysis dataset(s) will be a subset of the mass balance population.

All enrolled subjects will be used for the mass balance data listings. The mass balance population will be used for the analysis of the mass balance concentration data and the provision of mass balance tables and figures. The mass balance analysis dataset(s) may be used instead of the mass balance population for generation of mass balance tables and figures or to generate additional mass balance tables and figures. Where possible, this decision will be documented at the same time as the mass balance population and mass balance analysis dataset(s).

7 Subject Disposition, Demographics and Baseline Characteristics

No formal statistical testing will be performed on subject disposition, or on demographic or baseline data. Summaries of subject disposition and analysis populations will be based on all subjects and summaries of all other data described in this section will be based on the safety population, unless otherwise stated.

7.1 Screening Failures

Data for subjects who have failed screening will be databased but will not be subjected to data cleaning and therefore will not be reported, ie will not be included in the STDM or ADaM datasets, or any of the TFLs or the CSR.

7.2 Subject Disposition and Withdrawals

The number and percentage of subjects enrolled, dosed (in Part 1 and Part 2 separately), completed and discontinued will be presented overall. If any subjects discontinued from the study early then the number of subjects for each reason for discontinuation will be presented overall. However, if none of the subjects discontinued from the study early, then the reasons for discontinuation will not be populated in the summary table.

Subject disposition and withdrawal data will be listed including details of informed consent.

Protocol deviations and any violations of the inclusion/exclusion criteria will also be listed.

7.3 Analysis Populations

A single summary table will be produced detailing the number and percentage of subjects in each population for each study part (for safety and PK populations) and overall (for safety, PK and mass balance populations). The reasons for exclusion from each population will also be included in the summary.

Details of subjects included and excluded in the different analysis populations will be listed.

7.4 Analysis Datasets

If applicable, a summary table per population will be produced detailing the number and percentage of subjects in each analysis dataset for each study part and overall, as required. The table will be based on the relevant population the dataset is a subset of (ie the PK or mass

balance population). The reasons for exclusion from each dataset will also be included in the summary.

Details of subjects included and excluded in the different analysis datasets will be listed.

7.5 Demographic Characteristics and Lifestyle Details

Demographic data (date of birth, ethnicity, race, sex, height [cm], weight [kg] and body mass index [BMI; kg/m²]) will be recorded at screening. Note: Weight is also recorded at admission to Part 2, this data will be listed but not summarised (see Section 10.7). Age will be calculated using the following formula:

$$\text{Age (years)} = \frac{\text{Date of first dose of IMP} - \text{date of birth}}{365.25}$$

and will be rounded down to the nearest year (using the SAS Software floor function). If any subjects are enrolled but not dosed and had other assessments recorded, age will be calculated using the date of informed consent.

Summary statistics (number of subjects with an observation [n], mean, standard deviation [SD], median, minimum and maximum) will be presented overall for age at first dose and for height, weight and BMI at screening. The number and percentage of subjects will be presented overall for race, ethnicity and sex. The denominator for the percentage is all subjects in the safety population. If any values are missing, a “missing” row will be presented on the table.

Lifestyle details (ie smoking history [does the subject smoke, use e-cigarettes or use nicotine replacement products?] and alcohol consumption) will be summarised overall as a categorical variable.

Demographic and lifestyle data for all subjects will be listed.

7.6 Medical/Surgical History

Medical/surgical history will be recorded for each subject at the screening visit and updated at admission to each study part. All medical/surgical history data will be listed by subject.

7.7 Prior and Concomitant Medication

Medications (drug name) will be coded using the World Health Organisation (WHO) Drug Dictionary Global Drug Reference (2019 Q1 version or more recent version) using the following Anatomical Therapeutic Chemical (ATC) classification codes:

- product name
- preferred name
- drug code
- therapeutic subgroup (ATC 2nd level name and code)
- chemical subgroup (ATC 4th level name and code)

Prior medications are defined as medications that starts and stop prior to the first dose of IMP. All other medications will be defined as concomitant medications including those that start prior to the first dose of IMP and continue thereafter. Any medications with an unknown start or stop date will be assumed to be concomitant medications unless a partial start or stop date indicates otherwise.

All medications, including coded terms, will be listed. One combined data listing of prior and concomitant medications will be provided. All prior medications as defined above will be flagged with a "#" symbol. Within this flagged group, medications that started after screening and stopped before dosing of IMP will also be flagged using a "*" symbol.

7.8 Other Baseline Characteristics

All other baseline characteristics, as listed below, at screening and on admission (unless otherwise stated) for each part (as appropriate) will be listed by subject for all subjects:

- carbon monoxide breath test
- urine drug screen
- alcohol breath test
- virology (screening only)
- creatinine clearance (screening only)

8 Efficacy

Not applicable.

9 Pharmacokinetics and Mass Balance

9.1 Pharmacokinetic Parameter Estimation

The PK parameters for [¹⁴C]-KD025 (Part 1 IV dose), KD025 (Oral dose in Part 1 and Part 2), KD025m1 (Part 2) and KD025m2 (Part 2) and total radioactivity (Part 2) in plasma will be estimated where possible and appropriate for each subject using Phoenix WinNonlin software (v8.0 or a more recent version, Certara USA, Inc., USA).

9.1.1 Definition of Pharmacokinetic Parameters

Plasma PK parameter definitions and reporting specifications are provided in Table 2.

Table 2 Plasma Pharmacokinetic Parameters and Reporting Specifications

Parameter	Definition	Unit	DP or SF	No. of DP/SF	Study Part
Tlag	Time prior to the first measurable (non-zero) concentration (oral administration only)	h	DP	2	1 + 2
Tmax	Time of maximum observed concentration	h	DP	2	1 + 2
Cmax	Maximum observed concentration	mass unit/mL	SF	3	1 + 2
AUC(0-last)	Area under the curve from 0 time to the last measurable concentration	mass unit.h/mL	SF	3	1 + 2
AUC(0-inf)	Area under the curve from dosing extrapolated to infinity	mass unit.h/mL	SF	3	1 + 2
AUCextrap	Percentage of AUC(0-inf) extrapolated beyond the last measurable concentration	%	DP	2	1 + 2
T1/2	Apparent terminal elimination half-life	h	DP	2	1 + 2
lambda-z	The first order rate constant associated with the terminal (log-linear) portion of the curve	1/h	DP	4	1 + 2
CL	Apparent total body clearance after intravenous administration	mL/min	SF	3	1

Parameter	Definition	Unit	DP or SF	No. of DP/SF	Study Part
CL/F	Apparent total body clearance after extravascular administration, where F (fraction of dose bioavailable) is unknown	mL/min	SF	3	1 + 2 ^a
Vz	Apparent volume of distribution based on the terminal phase after intravenous administration	L	SF	3	1
Vz/F	Apparent volume of distribution based on the terminal phase after extravascular administration, where F (fraction of dose bioavailable) is unknown	L	SF	3	1 + 2 ^a
Vss	Predicted volume of distribution at steady-state after intravenous administration	L	SF	3	1
MRT(0-inf)	Mean residence time extrapolated to infinity (after IV or extravascular administration)	h	DP	2	1 + 2
F Cmax	Absolute bioavailability of the oral formulation compared to IV based on Cmax	%	DP	2	1 + 2
F AUC(0-inf)	Absolute bioavailability of the oral formulation compared to IV based on AUC(0-inf)	%	DP	2	1 + 2
FreI Cmax	Relative bioavailability based on Cmax	%	DP	2	1/2 ^a
FreI AUC(0-inf)	Relative bioavailability based on AUC(0-inf)	%	DP	2	1/2 ^a
MPR Cmax	Metabolite to parent ratio based on Cmax	NA	DP	2	2
MPR AUC(0-inf)	Metabolite to parent ratio based on AUC(0-inf)	NA	DP	2	2
lambda-z lower ^b	Lower limit on time for values to be included in the calculation of Lambda-z	h	DP	2	1 + 2
lambda-z upper ^b	Upper limit on time for values to be included in the calculation of Lambda-z	h	DP	2	1 + 2

DP = decimal places

SF = significant figures

^a = only for KD025

^b = these values should be listed but omitted from the descriptive statistics

NA = not applicable

9.1.2 Rules for Pharmacokinetic Parameter Estimation

For Part 1, PK parameters for Treatment B will be calculated using times relative to the start of infusion. For Treatment A (Part 1) and Treatment C (Part 2), PK parameters will be calculated using times relative to the administration time of Treatment A and C, respectively.

The imputation of non-numerical or negative values reported in the input dataset will be performed as follows:

- pre-dose sample times will be entered as zero
- values that are below the limit of quantification (BLQ) obtained prior to the Cmax will be entered as zero
- values that are BLQ after the Cmax will be treated as missing
- should partial AUCs be required, then values that are BLQ after Cmax may be imputed as zero for these partial areas if lambda-z cannot be determined

- values that are quantifiable after at least 2 consecutive BLQ values after Cmax will be treated as missing for the calculation of PK parameters
- values that are reported as "No Result" (NR) or "No Sample" (NS) etc. will be treated as missing

PK parameters will be estimated using standard Phoenix WinNonlin methods, details of which may be found in the documentation accompanying the WinNonlin software package. The following constraints will apply:

Parameter Estimation	Constraint
Sampling times	Actual
Trapezoidal method	Linear up / Log down rule
Number of points used for lambda-z	At least 3, not including Cmax
Minimum requirements for AUC	At least 3 consecutive quantifiable concentrations
Dose	Oral: Nominal IV: Actual
Rounded dose level	3 Significant Figures

Prior to PK parameter estimation the bioanalytical data may be corrected to account for the proportion of administered [¹⁴C] material not measured due to the use of a [¹²C] LC-MS/MS analysis method. Data correction will only be performed if the [¹⁴C]-contribution exceeds 1% of the dose administered. If required, KD025, KD025m1 and KD025m2 bioanalytical data will be multiplied by the determined data correction factor in SAS by the lead statistical programmer (or designee).

Where possible, the terminal elimination rate constant (lambda-z) will be calculated for all subjects. The value of lambda-z will be determined by the slope of the regression line of the natural log transformed concentrations vs time.

The WinNonLin determined choice of data points for determination of lambda-z will be reviewed by the pharmacokineticist who may adjust the selection in order to provide a more appropriate fit. The choice of data points for determination of lambda-z for each profile will be confirmed following a documented peer review.

Absolute Bioavailability of KD025 (F) will be calculated for individual subjects where possible as follows:

$$F = \left\{ \frac{AUC \text{ or } Cmax \text{ (KD025 oral)}}{AUC \text{ or } Cmax \text{ ([14C] - KD025 IV)}} \times \frac{Dose(IV)}{Dose(oral)} \right\} \times 100$$

F will be calculated using Cmax and AUC(0-inf). If for any reason the AUC(0-inf) is not calculable (NC), then an alternative or additional AUC such as AUC(0-last) or an AUC over a partial area may be used to calculate F.

The following comparisons will be made:

- absolute bioavailability tablet (Treatment A vs Treatment B)
- absolute bioavailability capsule (Treatment C vs Treatment B)

Non-dose-corrected relative bioavailability (Frel) will be calculated for individual subjects where possible as follows:

$$Frel = \left\{ \frac{\text{AUC or Cmax (test)}}{\text{AUC or Cmax (reference)}} \right\} \times 100$$

Frel will be calculated using Cmax and AUC(0-inf). If for any reason the AUC(0-inf) is not calculable then an alternative or additional AUC such as AUC(0-last) over a partial area may be used to calculate Frel.

The following comparisons will be made, where tablet dosing [Treatment A] is considered the reference):

- relative bioavailability capsule versus tablet (Treatment C vs Treatment A)

In Part 2, metabolite to parent ratios (MPR) will be calculated as follows using AUC(0-inf) and Cmax. If for any reason the AUC(0-inf) is not calculable then an alternative or additional AUC such as AUC(0-last) may be used:

$$MPR = \frac{\text{AUC or Cmax (metabolite)}}{\text{AUC or Cmax (parent)}} \times \frac{\text{MW (parent)}}{\text{MW(metabolite)}}$$

Correcting for molecular weight (MW):

- KD025 MW = 452.52 g/mole
- KD025m1 MW= 410.44 g/mole
- KD025m2 MW = 411.42 g/mole

In addition, for Part 2, total radioactivity whole blood to plasma ratios will be determined using SAS by the Lead Statistical Programmer (or designee) at the time points defined in the protocol for whole blood total radioactivity sampling. If the blood and/or plasma concentration values are BLQ (ie less than the lower limit of quantification [LLOQ]) at any given time point, then the ratio will not be calculated.

When converting whole blood collection weights to blood volume (if required) for the calculation of the whole blood to plasma ratios, the following conversion factor will be used:

$$1.06 \text{ g of blood} = 1 \text{ mL of blood}$$

This will be calculated in SAS as follows:

$$\text{Blood weight (g) / 1.06} = \text{Blood volume (mL)}$$

Alternatively, where total radioactivity concentrations in whole blood have been provided in mass unit/g units the following conversion will be performed using SAS:

$$\text{Concentration (mass units/g)} * 1.06 = \text{Concentration (mass units/mL)}$$

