5.3 Previous Study Findings

5.3.1 Non-clinical Data Summary

Nonclinical pharmacology studies demonstrate the potential of KD025 to have a therapeutic benefit in a number of indications, particularly in autoimmune disease through effects on Th17-type immune responses, and idiopathic pulmonary fibrosis (IPF) through anti-fibrotic mechanisms [12].

Solubility of KD025 is pH dependent ie, it is 100 µg/mL at pH 2.7, ~4 µg/mL at pH 6.5 and ~3 µg/mL at pH 7.4. The lower solubility at higher pH could potentially impact absorption of KD025 under physiological conditions.

KD025 plasma exposure generally increased with dose, was dose proportional or greater than dose proportional, and showed some accumulation. The elimination half-life of KD025 was variable in nonclinical studies with calculated values of approximately 2 h in mice, 1 to 7 h in rat and rabbit, and 1 to 3 h in dog.

KD025 undergoes first pass metabolism in all evaluated species after oral administration to form a ROCK2 active metabolite, KD025m1 and a metabolite that is relatively less active against ROCK2, KD025m2.

Distribution studies performed in rats with oral administration of carbon-14 [¹⁴C]-KD025 demonstrated distribution primarily into tissues associated with elimination (gastrointestinal [GI], liver, kidney, urinary bladder), adrenal gland, and exocrine glandular tissue. All tissues demonstrated clearance and no appreciable radioactivity was observed in the brain. Melanin-containing tissues (uveal tract and pigmented skin) demonstrated higher tissue retention, indicating some affinity of KD025 for melanin.

[¹⁴C]-KD025 excretion was similar in male and female rats and was predominantly via the faecal route (~90%), while urine accounted for a smaller proportion of excretion (<1%).

Based on in-vitro assessment, cytochrome P450 (CYP)3A4 and CYP1A2 were the predominant CYP isoforms responsible for the metabolism of KD025, although CYP2C8, CYP2D6 and Uridine 5'-diphospho-glucuronosyltransferase (UGT)1A9 may also contribute to a lesser extent. Metabolism of KD025 to KD025m1 was CYP3A4 and CYP2C8 dependent. Metabolism of KD025 to KD025m2 was CYP3A4 dependent with further metabolism of KD025m2 dependent on UGT1A1 with no to little contribution from CYP enzymes.

KD025 and the active metabolite KD025m1 is > 99% bound to human, dog and rat plasma proteins. KD025m2 is > 99% bound to human plasma protein.

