7.2 Endpoints

7.2.1 Primary Endpoints

- Absolute bioavailability (F) of KD025

- Mass balance recovery of total radioactivity in all excreta (urine and faeces): Ae, %Ae, Cum Ae and Cum %Ae
- Collection of plasma, urine and faeces for metabolite profiling and structural identification

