8.1 Study Plan

This is a single centre, non-randomised, open-label, two-part study in healthy male subjects. Six subjects will participate in both parts of the study.

8.1.1 Study Plan Part 1

Part 1 is an open-label, non-randomised single oral dose followed by an IV microtracer assessment in 6 healthy male subjects. On Day 1 subjects will receive a single dose of KD025 (Treatment A), in the fed state. Subjects will then receive an IV dose of [¹⁴C]-KD025 (100 µg, a 'microdose') containing NMT 37 kBq (1000 nCi) [¹⁴C], as a 15 min IV infusion (Treatment B), 1.75 h after the oral dose administration (Treatment A) ie, 15 min before the expected Tmax (2 h) for the oral dose.

Treatment	Investigational Medicinal Product (IMP)
A	KD025 Tablet, 200mg
B	[¹⁴ C]-KD025 solution for infusion, 20 µg/mL (100 µg in 5mL), containing NMT 37 kBq (1000 nCi) [¹⁴ C], as a 15 min IV infusion, 100 µg

¹⁴C: carbon-14, kBq: Kilobecquerel, IV: Intravenous, µCi: Microcurie, nCi: Nanocurie, NMT: Not more than.
All IMPs are described as free base equivalent.
Details of IMPs can be found in Section 5.2

It is planned to enrol 6 subjects so there are 4 evaluable subjects. An evaluable subject for Part 1 is defined as a subject who has sufficient data for evaluation of the primary bioavailability objective of the study.

All subjects will undergo preliminary screening procedures to determine their eligibility for Parts 1 and 2 of the study at the screening visit (Day -28 to Day -2 of Part 1). Subjects will be admitted to the clinical unit on the evening prior to IMP(s) administration (Day -1) for confirmation of eligibility and baseline procedures. Subjects will be dosed on the morning following admission (Day 1). Following an overnight fast (approximately 10 h), subjects will consume a standard breakfast and will receive a single dose of KD025 (Treatment A) 30 min after the start of breakfast. One hour and 45 min post Treatment A administration, subjects will receive an IV infusion of [¹⁴C]-KD025 solution (Treatment B). Subjects will remain resident in the clinic until up to 48 h post-oral dose (up to Day 3). The minimum washout period between dose administrations in Part 1 and 2 will be 7 days.

8.1.2 Study Plan Part 2

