4.3 Study Endpoints

4.3.1 Primary Endpoints

- absolute bioavailability (F) of KD025
- mass balance recovery of total radioactivity in all excreta (urine and faeces): Ae, %Ae, Cum Ae and Cum %Ae
- collection of plasma, urine and faeces for metabolite profiling and structural identification

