9.2 Pharmacokinetic Parameter Reporting Specifications

The following parameters will be reported for each study part and treatment where possible and appropriate, according to the reporting specifications provided in Table 2:

For plasma [¹⁴C]-KD025 following IV administration (Part 1)

Tmax, Cmax, AUC(0-last), AUC(0-inf), AUCextrap, T1/2, lambda-z, CL, Vz, Vss, MRT(0-inf)

For plasma KD025 following oral administration (Part 1)

Tlag, Tmax, Cmax, AUC(0-last), AUC(0-inf), AUCextrap, T1/2, lambda-z, CL/F, Vz/F, MRT(0-inf), F Cmax, F AUC(0-inf)

For plasma Total Radioactivity, KD025, KD025m1 and KD025m2 following oral administration (Part 2)

Tlag, Tmax, Cmax, AUC(0-last), AUC(0-inf), AUCextrap, T1/2, lambda-z, CL/F, Vz/F, MRT(0-inf), F Cmax, F AUC(0-inf), MPR Cmax, MPR AUC(0-inf)

Note: CL/F and Vz/F calculated for KD025 only.

For KD025 (Part 1/Part 2)

Frel Cmax, Frel AUC(0-inf)

The following flags/footnotes may be applied to the PK parameters:

Flag	Footnote
a	Rsq of regression was <0.9
b	Period used for regression analysis was less than 2-fold the calculated half-life
c	Extrapolated portion of AUC(0-inf) >20%
d	Insufficient post-Cmax data points for estimation of lambda-z
e	Entire profile BLQ, no pharmacokinetic parameters could be calculated
f	Quantifiable pre-dose values were observed, however were considered less than 5 % of Cmax

In the event that the Rsq of regression was <0.9 ('a' flag) or the extrapolated portion of AUC(0-inf) >20% ('c' flag), then lambda-z, AUC(0-inf) and the parameter estimates derived using lambda-z and/or AUC(0-inf), as appropriate, will be deemed unreliable and will be listed but excluded from the summary statistics.

In the event that the period used for regression analysis was less than 2-fold the calculated half-life ('b' flag), parameter estimates derived using lambda-z will be listed, flagged and included in summary statistics.

Additional flags may be applied based on emerging data.

In the event that quantifiable pre-dose values less than 5% of Cmax were observed, all parameter estimates for the profiles affected will be listed, flagged and included in summary statistics.

Note: in the event that quantifiable pre-dose concentrations greater than 5% of Cmax are observed, requirements for further action will be agreed with Kadmon and documented at the same time as the PK population. In this case, an additional flag would be defined.

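### The SAP gives the name of the primary endpoint, absolute bioavailability, to both an AUC ratio and a Cmax ratio; it ranks neither, and the Cmax ratio does not estimate F

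*SAP*

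**What the plan says.** Protocol 7.2.1 lists the primary endpoint as "Absolute bioavailability (F) of KD025", and SAP 4.3.1 repeats it as "absolute bioavailability (F) of KD025". Neither names an exposure metric. Protocol 15.3.2 lists a single parameter F, oral against IV, again without a metric.

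The SAP turns this one parameter into two. Section 9.1.2 has one formula that accepts either AUC or Cmax, followed by "F will be calculated using Cmax and AUC(0-inf". In Table 2 (Section 9.1.1), F Cmax is "Absolute bioavailability of the oral formulation compared to IV based on Cmax", and F AUC(0-inf) has the same definition with AUC(0-inf) in place of Cmax. Section 9.2 lists both for the Part 1 oral dose without ranking them. Section 12.2, on changes to planned analyses, covers only Tlag and AUCextrap.

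Two further rules bear on this. Under Section 9.2, if R-squared is below 0.9 (flag a) or more than 20% of AUC(0-inf) is extrapolated (flag c), the affected "parameter estimates derived using lambda-z and/or AUC(0-inf), as appropriate, will be deemed unreliable and will be listed but excluded from the summary statistics". Section 9.1.2 allows a substitute AUC on a narrower condition: "If for any reason the AUC(0-inf) is not calculable (NC), then an alternative or additional AUC such as AUC(0-last" or a partial-area AUC may be used.

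**The concern.** The CL/F and Vz/F rows of Table 2 use F to mean the bioavailable fraction of the dose. Under linear kinetics the dose-normalised oral-to-IV AUC ratio estimates that fraction. The corresponding Cmax ratio does not. Its numerator depends on how fast the drug is absorbed, and its denominator on how long the infusion lasts and how quickly the drug distributes. Changing the infusion length would change F Cmax while the true F stayed the same.

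As written, the clinical study report would contain two different numbers called absolute bioavailability, and nothing in the plan would say which answers the primary objective. The flag rules add to this. They can remove F AUC(0-inf) from the summary but never F Cmax, and the substitute AUC is not clearly available for a value that was calculated and then excluded. There are 6 subjects, data are wanted in at least 4 evaluable (Protocol 15.1), and there are no replacements (Protocol 8.4). The Cmax figure could therefore be summarised on more subjects than the valid one.

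**Working it through.** **Inputs from the documents**

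- Infusion length T = 0.25 h. It starts "15 min before the expected Tmax (2 h) for the oral dose" (Protocol 8.1.1), so oral Tmax is taken as 2 h.
- Doses in the treatment tables: 200 mg oral and 100 µg IV, a ratio of 200,000/100 = 2,000. This reproduces the 1/2000 in Protocol 6.2. The same section also mentions 1/1000; those statements need reconciling, but the dose ratio cancels below.
- Half-life: nonclinical values only, about 2 h in mice and "1 to 7 h in rat and rabbit, and 1 to 3 h in dog" (Protocol 5.3.1). Applying any half-life to humans is an assumption.

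The plan gives no value of F and no precision calculation, so there is no other figure to reproduce.

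**One compartment, no absorption lag**

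With k = ln 2 / half-life:

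- oral Cmax = F·D/V · exp(−k·Tmax)
- infusion Cmax = D/(V·k·T) · (1 − exp(−kT))
- so F_Cmax/F = exp(−k·Tmax) · kT/(1 − exp(−kT))

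| Assumed half-life (h) | exp(−2k) | kT/(1 − exp(−kT)) | F_Cmax/F |
|---|---|---|---|
| 1 | 0.250 | 1.089 | 0.272 |
| 2 | 0.500 | 1.044 | 0.522 |
| 3 | 0.630 | 1.029 | 0.648 |
| 5 | 0.758 | 1.017 | 0.771 |
| 7 | 0.820 | 1.012 | 0.831 |
| 12 | 0.891 | 1.007 | 0.897 |
| 24 | 0.944 | 1.004 | 0.947 |

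The 1 h row requires absorption slower than elimination (ka 0.347 against k 0.693 per h).

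The AUC version was checked by non-compartmental calculation on the flow-chart sampling times, using the SAP's linear-up/log-down rule plus extrapolation. For half-lives of 1 to 7 h, a true F of 100% comes back as 99.1% to 99.6%. F Cmax comes back as 27% to 83%.

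**Two compartments (all parameters assumed; ka solved for Tmax 2 h; true F 60%)**

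| CL, V1, Q, V2 (L/h, L, L/h, L) | ka (per h) | Terminal half-life (h) | F Cmax | F_Cmax/F |
|---|---|---|---|---|
| 10, 20, 20, 60 | 0.283 | 7.2 | 10.5% | 0.174 |
| 10, 30, 10, 60 | 0.441 | 9.5 | 20.0% | 0.333 |
| 20, 60, 10, 60 | 0.550 | 7.1 | 25.1% | 0.419 |
| 10, 50, 5, 50 | 0.805 | 11.8 | 35.0% | 0.583 |

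The AUC ratio is 60% in all four.

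**Infusion length alone**

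Moving T from 0.05 h to 2 h with F fixed moves F_Cmax/F from 0.760 to 0.868 (one compartment, 5 h half-life) and from 0.312 to 0.537 (second two-compartment row).

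**Direction**

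Suppose disposition is linear and concentration falls steadily after a bolus. The infusion delivers at a fractional rate of 1/0.25 = 4 per h. If the peak fractional oral input rate stays below that, oral Cmax per unit dose must be less than F times infusion Cmax per unit dose. First-order absorption with ka below 4 per h meets the condition, and every ka solved here lies between 0.28 and 2.19 per h.

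**When flag c would act**

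By one-compartment approximation, the extrapolated share exceeds 20% when exp(−k·t) > 0.20, that is, when half-life > t·ln 2/ln 5. For a last quantifiable time t of 12, 24 or 48 h, the threshold is 5.2, 10.3 or 20.7 h.

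**The case against.** The strongest reply is that little confusion would follow. The two parameters have different names, and each definition states its basis. Only the AUC version has a substitute rule, and nothing lets Cmax stand in for a missing AUC, so AUC priority can be inferred. The study is exploratory and descriptive, with no test or threshold, so no error rate is affected. All of this is fair and limits the weight of the point. It does not supply the missing designation, and it does not make the Cmax ratio an estimate of F. In a descriptive study the defined estimate is itself the result.

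The sizes can also be challenged. The two-compartment sets have no source in the documents, and the one-compartment formula ignores absorption lag although dosing is fed and Tlag is a planned parameter. With a 1 h lag the exponent becomes −k(2 − 1), and the ratio rises from 0.272 to 0.545 at a 1 h half-life and from 0.831 to 0.917 at 7 h. It stays below 1, so the direction stands and the size remains uncertain.

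The flag gap is the weaker part. At a 7 h half-life, flag c needs the last quantifiable sample before 7 × ln 5/ln 2 ≈ 16 h, while sampling runs to 48 h and Protocol 6.2 expects concentrations well above the quantification limit. No estimate is available for flag a. Excluded values are still listed, and AUC(0-last) is still reported. This part is a request for clarification, and the main point does not depend on it.

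**Conclusion.** The concern holds. Followed as written, the SAP yields a number that carries the primary endpoint's name and does not estimate it, and the SAP does not say which of the two is primary. The primary objective is not lost, because F AUC(0-inf) is planned and valid.

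Given linear kinetics, a concentration that declines after a bolus, and oral input slower than the infusion, F Cmax understates F. How far it does so cannot be fixed from the documents, which contain no human half-life or distribution data. The illustrative range is 0.27 to 0.95 of true F for one compartment with half-lives of 1 to 24 h and no lag, and 0.17 to 0.58 for the four assumed two-compartment cases. There is no consequence for alpha or power.

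**What to change.** - In SAP 9.1.2, state that the primary endpoint F is the dose-normalised AUC(0-inf) ratio for the tablet against IV (Treatment A versus B, Part 1), and take Cmax out of the F formula.
- Delete F Cmax, or keep it in Table 2, 9.1.2 and 9.2 as a dose-normalised oral-to-IV Cmax ratio with a note that it does not measure absolute bioavailability. Designating the AUC ratio and relabelling is enough; deletion is optional.
- Keep the existing substitution of AUC(0-last) or a partial-area AUC. State whether it also applies when AUC(0-inf) is calculated but excluded under flag a or c.
- Leave Frel Cmax as it is, since both treatments in that comparison are oral.

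The cost is a few sentences of SAP text and a table label. Sampling, procedures and data collection do not change.
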